6.4. Discussion of Study Design, Including Choice of Control Group

The heterogeneity of signs, symptoms, and key phenotypic features (eg, age at onset, rate of progression, and survival duration) in patients with PKAN is a critical consideration in designing a clinical study for this disease. Placebo-control is necessary to control for variability in disease

severity and rate of progression. A randomized, placebo-controlled, parallel design study allows for a balanced distribution of uncontrolled variables across randomized groups, and a rigorous assessment of true drug effects on the outcome variables, controlling for nonspecific effects.

Demonstration of a clinically meaningful treatment effect over a 24-week period is sufficient to establish fosmetpantotenate as safe and efficacious for the treatment of PKAN, as there are no effective treatments available to date for this debilitating disease. The double-blind period of the trial will evaluate the efficacy of fosmetpantotenate in improving signs, symptoms, and functioning in patients with PKAN, and the safety extension will evaluate whether these improvements are generally maintained during an open-label treatment period that aims to simulate more real-world therapeutic conditions (eg, concomitant medications, which are fixed during the 24-week double-blind period, may be adjusted during the open-label extension based on medical judgment).

6.5. Dosing Considerations

Investigational product will be prepared and administered by site personnel, together with the patient and/or family, during in-clinic patient visits in order to provide training in proper administration. Following adequate training, doses may be self-administered by the patient or caregiver at the site's discretion.

All investigational product should be taken with food. If necessary, investigational product may be given through a feeding tube.

Details regarding dosing can be found in the study manuals.

6.5.1. Dose Selection Rationale

A dose of 900 mg fosmetpantotenate daily, administered as 300 mg TID with food, will be used in this study for adult patients (18 and older) and pediatric patients weighing 40 kg or more.

Two lower dose strengths will be used for pediatric patients weighing less than 40 kg. For pediatric patients weighing at least 20 kg but less than 40 kg, a dose of 450 mg daily, administered in 3 equally divided doses of 150 mg (TID) with food, will be used. For pediatric patients weighing less than 20 kg, a dose of 225 mg daily, administered in 3 equally divided doses of 75 mg (TID) with food, will be used.

In the Phase 1 healthy adult volunteer studies (Studies 024HVOL14004, 024HVOL15007, and 024HVOL15008), fosmetpantotenate was safe and well tolerated at single oral doses up to 1800 mg, with no identifiable dose-related safety findings (see also [Section 4.1](#)). A dose of 3600 mg was associated with mostly mild gastrointestinal AEs. Administration of 300 mg fosmetpantotenate with a high-fat meal resulted in greater exposure and longer overall exposure time, without an increase in maximum fosmetpantotenate concentration (C_{max}).

PKAN is characterized by a large number of genotypic mutations of the *PANK2* gene that have an unclear relationship with phenotypic manifestations. Earlier-onset, rapidly progressive PKAN may be associated with decreased functionality of the Pank2 enzyme ([Hartig, 2006](#)); thus, higher doses than those used to date in patients with PKAN may be required in some patients to produce a treatment effect. A dose of 300 mg TID with food (900 mg daily), is therefore being used in

this study. The 300 mg dose was safe and well tolerated in both fed and fasted states in a Phase 1 food effect study.

Single-dose data from the Phase 1 studies also showed the absence of a relationship between blood exposure and any safety related signal until a dose of 3600 mg was used; additionally, no SAEs were reported in the studies. Therefore, of primary practical importance for this pivotal study was the selection of a dose that will be safe in pediatric patients, while showing efficacy for as many of these patients as possible.

The overall safety profile of fosmetpantotenate to date suggests that a weight-based pediatric dosing strategy, which facilitates ease of use for patients and their caregivers, is medically reasonable.

The mean weight for a normal 11 ½- to 12-year-old in the United States (US) is approximately 40 kg (Kuczmarski, 2002). However, patients under the age of 12 years, as well as adolescent patients who are underweight due to developmental delay or other nutritional and metabolic effects of PKAN, are likely to weigh less than 40 kg. In addition, patients ages 6 or older will be enrolled in this trial, who will likely also weigh less than 40 kg. Thus, for pediatric patients weighing less than 40 kg but at least 20 kg, the 900 mg daily dose (300 mg TID) will be reduced by 50% to 450 mg daily (150 mg TID). For the few pediatric patients weighing <20 kg, the dose will be reduced by an additional 50% to 225 mg daily (75 mg TID). The conservative dosing approach outlined here reduces the daily fosmetpantotenate dose by approximately 2-fold relative to adults in children weighing less than 40 kg, and an additional 2-fold in children weighing less than 20 kg.

6.5.2. Dose Initiation

6.5.2.1. Double-Blind Period

The double-blind period will begin with dose escalation for Days 1 through 3, followed by the full dose (TID) starting on Day 4. Dose escalation on Days 1 through 3 will proceed as follows, based on the patient's age and weight at screening:

Patients aged 18 to 65 years and patients aged 6 to <18 years weighing ≥40 kg: On Day 1, patients will receive one 300 mg dose (in the morning); on Days 2 and 3, they will receive 300 mg twice daily (BID, at least 8 hours apart) for a total daily dose of 600 mg; and on Day 4, they will receive the full dosage of 300 mg TID (given at approximately 8 hour intervals) for a total daily dose of 900 mg.

Patients aged 6 to <18 years weighing ≥20 kg but <40 kg: On Day 1, patients will receive one 150 mg dose (in the morning); on Days 2 and 3, they will receive 150 mg BID (at least 8 hours apart) for a total daily dose of 300 mg; and on Day 4, they will receive the full dosage of 150 mg TID (given at approximately 8 hour intervals) for a total daily dose of 450 mg.

Patients aged 6 to <18 years weighing <20 kg: On Day 1, patients will receive one 75 mg dose (in the morning); on Days 2 and 3, they will receive 75 mg BID (at least 8 hours apart) for a total daily dose of 150 mg; and on Day 4, they will receive the full dosage of 75 mg TID (given at approximately 8 hour intervals) for a total daily dose of 225 mg.

6.5.2.2. Open-Label Period

Patients will receive open-label fosmetpantotenate after they complete the double-blind period of the study. No dose escalation is required for the open-label period. All patients (regardless of randomization assignment for the double-blind period) will initiate treatment with fosmetpantotenate in the open-label period according to the dose of study medication they were receiving at the end of the double-blind period; for patients 6 to <18 years of age, the initial dose may be adjusted, if needed, based on the patient's weight at the end of the double-blind period.

For patients 6 to <18 years of age, the dose will be adjusted as needed during the open-label period based on their weight taken at study visits every 24 weeks.

6.5.3. Dose Modification

Elective dose reductions for safety or tolerability reasons only are allowed, and only 1 time, throughout the first 6 weeks of the double-blind period of the study, according to the following schedule:

- Patients 18 to 65 years of age or 6 to <18 years of age and weighing ≥ 40 kg: the 300 mg TID dose may be reduced to 150 mg TID
- Patients 6 to <18 years of age and weighing ≥ 20 kg but <40 kg: the 150 mg TID dose may be reduced to 75 mg TID
- Patients 6 to <18 years of age and weighing <20 kg: the 75 mg TID dose may be reduced to 75 mg once daily

Patients who are unable to tolerate the reduced dose will be discontinued from treatment. The Investigator should attempt to increase the dose back to the patient's assigned fixed dose as safety and tolerability allow.

Once patients have been treated in the open-label period for at least 24 weeks, and after the second DMC review has occurred, dose increases of 1 level will be allowed for perceived lack of efficacy. Dose increases will only be allowed following consultation between the Investigator, the Medical Monitor, and the Sponsor, and only to the maximum dosage of 300 mg TID. Elective dose reductions for safety or tolerability reasons only are allowed, and only 1 time, throughout the first 6 weeks of the open-label period of the study.

Fosmetpantotenate will not in any case be used as a rescue medication.

6.5.4. Interruption and Discontinuation of Study Medication

6.5.4.1. Temporary Interruption of Study Medication

Patients who temporarily interrupt prior to completion of the study, will continue with study visits and assessments according to the schedule of study events ([Section 15.1](#)). Unless contraindicated, treatment should be resumed whenever possible (including between visits), and treatment resumption should be considered at every visit following study medication interruption. If the patient's dose was reduced prior to the temporary interruption, the study medication should be resumed at the reduced dose and the Investigator should attempt to increase the dose back to the patient's assigned fixed dose as safety and tolerability allow.

6.5.4.2. Permanent Discontinuation of Study Medication

A patient's investigational product may be discontinued at any time at the patient's/parent's/legal guardian's request or at the discretion of the Investigator, the Medical Monitor, or the Sponsor. Justifiable reasons for the Investigator or the Sponsor to discontinue a patient from treatment may include, but are not limited to:

- The patient experiences any AE, clinically significant laboratory abnormality, or intercurrent illness, or other medical condition that indicates to the Investigator that continuation on study medication is not in the best interest of the patient (adverse event).
- A significant protocol violation (ie, patient failed to meet entry criteria or did not comply with protocol requirements resulting in an unacceptable risk to the patient's health) (protocol deviation).
- Noncompliance with study medication (non-compliance with study drug).
- Patient or parent/legal guardian decision to stop study medication (withdrawal by parent/guardian).
- Investigator discretion (physician decision).
- The patient participates in another investigational study without the prior written authorization of the Sponsor or its designee (protocol deviation).
- The patient becomes pregnant (pregnancy); study medication must be discontinued immediately once the patient becomes aware of the pregnancy and the investigator must be notified of the pregnancy (pregnancy) (see also [Section 10.6](#), Pregnancy Reporting).
- The patient's concomitant PKAN maintenance medications/therapies are adjusted during the double-blind period (protocol deviation).
- Patient is lost to follow-up (lost to follow-up).

Decisions to prematurely discontinue patients from study medication should be reviewed by the Investigator, the Medical Monitor, and the Sponsor.

Patients who permanently discontinue study medication early should be encouraged to continue study visits through Week 120 for continued collection of safety and efficacy data despite stopping study medication, but may withdraw consent at any time (see [Section 6.3.3](#)). Patients who agree to continue regularly scheduled study visits will complete the End of Treatment assessments listed in the schedule of events ([Section 15.1](#)) as close as possible to the patient's last dose of study medication. The visit data, including the primary reason for discontinuation of study medication, will be recorded on the End of Treatment eCRF. Subsequent study visit data will be recorded on the visit-specific eCRF, and the patient's final study visit will be recorded on the End of Treatment/Early Termination eCRF.

For patients who permanently discontinue study medication, the Investigator should resume standard of care treatment, including treatment with appropriate medications, as deemed necessary.

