6.3. Completion of a Patient’s Participation in the Study and Overall Study Completion

6.3.1. Completion of a Patient’s Participation in the Study

Each patient will participate in the study for approximately 4 weeks during the screening phase, followed by 24 weeks of double-blind treatment and 278 weeks of open-label treatment. At the end of the open-label treatment period, study medication will be discontinued, and patients will be contacted by phone for a safety review 4 weeks later. Thus, patients will participate for a total of approximately 310 weeks.

A patient will be considered as having completed the study, regardless of whether the patient is on or off study medication, if the patient is followed until Week 302 or if rolled off early onto commercial product, whichever happens first. Patients who successfully complete the study will complete the Week 302 assessments listed in the schedule of events ([Section 15.1](#)). The visit

data, including final disposition of the patient, will be recorded on the End of Treatment /Early Termination electronic case report form (eCRF).

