6.3.3. Premature Discontinuation from the Study

In general, patients should be encouraged to both stay on study medication and remain in the study until study termination/completion. However, patients or their parents/guardians are free to withdraw consent/assent and/or discontinue the patient's participation in the study at any time, without prejudice to subsequent standard of care treatment. A patient's participation in the study may also be discontinued at any time at the discretion of the Investigator or the Sponsor.

Reasons for premature discontinuation from the study may include:

- Death
- Voluntary withdrawal of patient/guardian assent/consent (complete withdrawal of consent requires a patient's/parent's/guardian's refusal of ALL methods of follow-up noted in the informed consent form: procedures, participation in reduced procedures/study visits, telephone/alternative contact only, source document or designated alternative contact, or access to medical records from alternative sources)
- Termination of the study by the Sponsor, or any regulatory authorities (see [Section 13.4.5](#))
- Lost to follow-up
 - The Investigator must make every effort to contact patients who fail to return for scheduled visits so that they will not be declared "lost to follow-up."
 - Patients will be considered "lost to follow-up" only after reasonable, documented attempts to reach the patient prove unsuccessful. "Reasonable" is defined as at least 3 phone calls and a certified letter. This information and dates of attempted contact must be recorded in the patient's source documents.

A patient who chooses to not continue regularly scheduled study visits (ie, withdraws consent) will complete the Early Termination assessments listed in the schedule of events ([Section 15.1](#)) as close as possible to the patient's last dose of study medication. The visit data, including the primary reason for premature discontinuation from the study, will be recorded on the Early Termination eCRF. Post-study SAEs will be reported according to [Section 10.5.2](#).

Decisions to prematurely discontinue patients from the study will be reviewed by the Investigator, the Medical Monitor, and the Sponsor.

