Visit	V12	V13	V14	V15	V16	V17	V18	V19	V20	V21	V22- V28 ¹³	Unsched Visit ¹	End of Treatment/ Early Termination Visit/Final Contact ²
Study Week	W27 ± 7D	W30 ± 7D	W36 ± 7D	W48 ± 7D	W60 ± 7D	W72 ± 7D	W84 ± 7D	W96 ± 7D	W108 ± 7D	W120 ± 7D	W146, W172, W198, W224, W250, W276, W302 ± 7D		
Weight		X	X	X		X		X		X	X		X
Height (if <18 years of age at enrollment)		X				X				X	X		X
C-SSRS ³		X	X	X	X	X	X	X	X	X	X		X
Abbreviated physical examination ⁴		X	X	X		X		X		X	X		X
Vital signs ⁵	X	X	X	X	X	X	X	X	X	X	X		X
12-Lead electrocardiogram ⁵		X	X	X		X		X		X	X		X
Hematology ⁶	X	X	X	X		X		X		X	X		X
Chemistry ⁶	X	X	X	X		X		X		X	X		X
Coagulation ⁶		X								X	X		X
Urinalysis ⁶		X	X	X		X		X		X	X		X
Urine pregnancy ⁷		X*	X*	X*		X							
PKAN-ADL		X	X	X	X	X	X	X	X	X	X		X
UPDRS Part III		X	X	X	X	X	X	X	X	X	X		X
BAD scale				X		X		X		X	X		X
CGI-I		X	X	X	X	X	X	X	X	X	X		X
25-foot walk test ⁸			X	X		X		X		X	X		X
Neuro-QoL Adult/Pediatric (upper and lower extremity) ⁹			X	X		X		X		X	X		X
EQ-5D-3L/EQ-5D-Y ⁹				X		X		X		X	X		X
FIM/WeeFIM ⁹				X		X		X		X	X		X

Visit	V12	V13	V14	V15	V16	V17	V18	V19	V20	V21	V22- V28 ¹³	Unsched Visit ¹	End of Treatment/ Early Termination Visit/Final Contact ²
Study Week	W27 ± 7D	W30 ± 7D	W36 ± 7D	W48 ± 7D	W60 ± 7D	W72 ± 7D	W84 ± 7D	W96 ± 7D	W108 ± 7D	W120 ± 7D	W146, W172, W198, W224, W250, W276, W302 ± 7D		
Diadochokinetic Assessments ¹⁰				X		X		X		X	X		X
Pharmacokinetic sampling ¹¹		X											
Blood sample collection ¹⁴	At Selected Sites Only: 1 Blood sample ¹⁵												
Investigational product dispensing/accountability		X	X	X	X	X	X	X	X	X ¹²	X ¹²		X ¹²
AE Assessment	Continuous Monitoring												▶
Conmeds/therapies	Continuous Monitoring												▶

Abbreviations: AE = adverse event; BAD = Barry Albright Dystonia; CGI-I = Clinician Global Impression of Improvement; Con meds = concomitant medications; C-SSRS = Columbia Suicide Severity Rating Scale; D = Day; EQ-5D-3L/ EQ-5D-Y = EuroQol 5-dimension, 3-level quality of life instrument/EuroQol-5D Youth Version; FIM/WeeFIM = Functional Independence Measure/Functional Independence Measure for Children; Neuro-QoL = quality of life measure for adults/children with neurological disorders; PK = pharmacokinetic; PKAN-ADL = Pantothenate Kinase-associated Neurodegeneration Activities of Daily Living; Unsched = unscheduled UPDRS = Unified Parkinson’s Disease Rating Scale; V = Visit; W = Week

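### The protocol gives two follow-up horizons for patients who stop study drug: Week 120 in Section 6.5.4.2, but Week 302, on or off drug, in the completion definition of Section 6.3.1

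*Protocol*

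**What the plan says.** Protocol Section 6.5.4.2 covers permanent discontinuation of study medication. It says these patients "should be encouraged to continue study visits through Week 120 for continued collection of safety and efficacy data", and adds that they may withdraw consent at any time. No other sentence in the protocol deals specifically with how long patients who have permanently stopped drug should be followed.

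Three other places give a later horizon:

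- **Section 6.3.1** sets the completion rule. It applies whether or not drug is still being taken, and it is met "if the patient is followed until Week 302 or if rolled off early onto commercial product, whichever happens first". Those who complete are to have the Week 302 assessments.
- **Section 6.3.3** says that "patients should be encouraged to both stay on study medication and remain in the study until study termination/completion".
- **Table 15.1-2** (Appendix A) schedules the later open-label visits at "W146, W172, W198, W224, W250, W276, W302 ± 7D". Neither the table nor its footnotes limit these visits to patients on drug. Section 6.2 gives the same visit weeks, with safety phone calls every 13 weeks between site visits after Week 120.

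Section 6.5.4.1 keeps patients who interrupt drug temporarily on the full schedule of events.

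**The concern.** A site with an off-drug patient will look to Section 6.5.4.2, find Week 120, and have a reason to end visits there. By Section 6.3.1 that patient has not completed the study. Another site, reading Section 6.3.1 or 6.3.3, would carry a similar patient to Week 302. Follow-up length and completion status would then depend on which section the site read.

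This matters for three reasons.

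- **Selection.** SAP Section 4.12 gives long-term safety as the main objective of the extension. Section 6.5.4.2 lists adverse events and patient decision among the reasons for stopping drug. If off-drug patients tend to leave at Week 120, later by-visit summaries lean towards patients who tolerated the drug or felt they benefited. A mean change in PKAN-ADL over the extension would then mix a drug effect with a change in who is measured.
- **Disposition.** Protocol Section 12.5 and SAP Section 4.5 report study discontinuation by reason. Patients who did what Section 6.5.4.2 asked may appear there as discontinuations.
- **Safety reporting windows.** Section 10.5.1 collects adverse events to 30 days after the last dose or the last scheduled visit, whichever is later. Section 10.5.3 can end adverse event follow-up when participation is complete. Section 10.5.2 ties its post-study rule for serious events to completion as defined in Section 6.3.1. For an off-drug patient each of these turns on whether the end point is Week 120 or Week 302.

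**Working it through.** **Inputs**

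| Quantity | Value | Source |
|---|---|---|
| Screening | about 4 weeks | Protocol 6.3.1 |
| Double-blind period | 24 weeks | Protocol 6.3.1 |
| Open-label period | 278 weeks | Protocol 6.3.1 |
| Safety call after end of treatment | 4 weeks later | Protocol 6.3.1 |
| Completion point, on or off drug | Week 302 | Protocol 6.3.1 |
| Horizon for permanently off-drug patients | Week 120 | Protocol 6.5.4.2 |
| Open-label site visits to Week 120 | W27, 30, 36, 48, 60, 72, 84, 96, 108, 120 (10 visits) | Table 15.1-2 |
| Open-label site visits after Week 120 | W146, 172, 198, 224, 250, 276, 302 (7 visits) | Table 15.1-2 |

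**Step 1: reproduce the plan's timeline.**

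- End of treatment: 24 + 278 = 302 weeks.
- Total participation: 4 + 24 + 278 + 4 = 310 weeks.

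Both match the protocol. The timeline is consistent, and Week 120 is the one horizon that does not fit it.

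**Step 2: size of the gap.**

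- Weeks: 302 − 120 = 182.
- Share of the open-label period: 182 / 278 = 65%.
- Site visits: 7 of 10 + 7 = 17, or 41%.
- Phone calls: 182 / 26 = 7 intervals between site visits, with one 13-week call in each, so 7 calls. These calls also collect PKAN-ADL, adverse events and concomitant medication.

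**Step 3: how the sections treat an off-drug patient.**

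| Situation | 6.5.4.2 | 6.3.1 |
|---|---|---|
| Stops drug before Week 120, leaves after the Week 120 visit | Guidance met | Not a completer, unless rolled off onto commercial product |
| Stops drug before Week 120, stays to Week 302 | Guidance exceeded, not forbidden | Completer |
| Stops drug after Week 120 (for example Week 200) | Named horizon already past, so no guidance | Completer if followed to Week 302 |

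The first row is the conflict. The third row is a related gap: read literally, the Week 120 wording gives no horizon at all to a patient who stops later.

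**Step 4: reach.** Week 120 and Week 302 both lie well beyond Week 24, so the primary and secondary efficacy analyses, their power and their type I error do not depend on either.

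**The case against.** The strongest reply is that Section 6.5.4.2 encourages and does not cap. That stands, and it rules out several stronger readings that a reader might infer:

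- *That off-drug follow-up must end at Week 120.* The section does not tell sites to stop visits, and Section 6.3.3 encourages patients in general to remain.
- *That an off-drug patient can never complete.* Section 6.3.1 says the opposite for anyone followed to Week 302.
- *That visits after Week 120 are reserved for patients on treatment.* No text says so. Selective late data are a likely practical effect, not a rule of the plan.
- *That a patient leaving at Week 120 fits no discontinuation reason.* The list in Section 6.3.3 is open-ended, and the section also allows discontinuation at the discretion of the investigator or sponsor. Such a patient can be classified. What is missing is a statement of how.
- *That a number of lost patients can be given.* The documents state no open-label stopping rate. Patients who stop drug after Week 120 would also have contributed to some later visits first.

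It is also fair that the consequence is limited. Open-label efficacy is exploratory, is confined to listings in the interim report, and awaits a later SAP version (SAP Sections 4.10, 4.10.4 and 4.12.1). SAP Section 4.5 specifies a completer count for the double-blind period alone, so no planned Week 302 completer row is wrong as it stands.

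None of this reconciles the sections. Naming an end point in the one sentence written for these patients invites sites to use it.

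**Conclusion.** The inconsistency is real and in current text. An off-drug patient who follows the Week 120 guidance and goes no further ends follow-up 182 weeks (65% of the open-label period) and 7 of 17 open-label site visits short of the completion point, and does not meet the completion definition unless rolled off early onto commercial product. Data after Week 120 may therefore come selectively from patients still on drug, in an extension whose main aim is long-term safety.

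The size of the gap is arithmetic on the documents' own figures. The selection effect rests on two assumptions: that sites treat Week 120 as the end point, and that stopping drug is related to tolerability or perceived benefit. Its direction is likely but not certain, and its size cannot be estimated from the documents.

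A reader might infer that Week 120 is left over from a shorter extension. The visit pattern changes there, and in Table 15.1-2 the Week 120 dispensing cell carries footnote 12, which describes no dispensing at Week 302 or early termination. That is suggestive, not proof.

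The point should be corrected, but it does not touch the Week 24 analyses.

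**What to change.** State one follow-up horizon for patients who permanently stop drug, including those who stop after Week 120. Which horizon is intended is for the sponsor to settle.

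- **Simplest option:** in Section 6.5.4.2, change the horizon from Week 120 to Week 302, to match Sections 6.3.1 and 6.3.3 and Table 15.1-2. The text change is one phrase, through a protocol amendment under Section 13.3. The running cost is at most 7 site visits and 7 calls, all already scheduled, for each off-drug patient who agrees to stay.
- **If Week 120 is intended:** amend Section 6.3.1 to say how off-drug patients leaving at Week 120 are classified, and carry that into the disposition tables. The later SAP version should state that summaries after Week 120 leave out most patients who stopped drug. Calling those summaries on-treatment would be inaccurate, because temporarily interrupted patients and any off-drug patients who stay would still be in them. This option costs wording only, but it accepts the selective late data.

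Either change is timely, because the open-label efficacy analysis has yet to be specified in full.
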